5.2.3. Efficacy Evaluable (EE) Population

EE population – all subjects who completed at least one cycle (CC-122) of their assigned treatment regimen and have a baseline and at least one post-baseline efficacy assessment. Subjects will be summarized under the treatment arm they were enrolled.

5.2.4. Pharmacokinetic (PK) Population

PK population - all subjects who have at least one measurable CC-122 and/or ibrutinib concentration datum. Subjects will be summarized under the actual dose level corresponding to the PK sample collection.

Intensive PK Population is defined as all subjects who have at least one measurable CC-122 concentration datum from intensive sampling. Intensive PK population will be used to support summaries for CC-122 PK concentrations and parameters from the intensive sampling.

6. SUBJECT DISPOSITION

The total number of subjects who are considered screen failures will be summarized.

A summary of subject disposition will be presented by treatment arm, and dose cohort.

A tabulated summary of all analysis populations in [Section 0](#) will be presented together with the subject disposition. A summary of Safety population subjects by site, treatment arm, dose cohort, and overall will be presented.

Reasons for discontinuation from the IP (CC-122, ibrutinib and obinutuzumab) will be summarized by treatment arm, dose cohort, and overall with the following categories:

- Progressive disease
- Adverse event
- Death
- Pregnancy
- Lack of efficacy
- Withdrawal by Subject
- Non-compliance with study drug
- Lost to follow up
- Study terminated by sponsor
- Transition to commercially available treatment
- Physician decision
- Disease relapse
- Symptomatic deterioration
- Protocol violation
- Start of a new anti-CLL therapy (with the exception of rituximab for the treatment of autoimmune hemolytic anemia) *
- Upon completion of a maximum of 24 cycles of CC-122 *
- For subjects on Arm B, subjects who have discontinued CC-122 prior to the maximum of 24 cycles and have received an additional 3 cycles of investigational supply of ibrutinib *
- Other

Note the three reasons marked with “*” are allowed for treatment discontinuation in Protocol Amendment 7 and will be derived using corresponding standard wordings from the text field for “Other” specified reason: ‘Start of new anti-CLL therapy’, ‘Maximum number of CC-122 cycles completed’, ‘CC-122 discontinued, additional 3 cycles of ibrutinib completed’.

Reasons for discontinuation from the study will be summarized by, treatment arm, dose cohort, and overall with the following categories:

- Death

- Adverse event
- Pregnancy
- Progressive disease
- Lack of efficacy
- Withdrawal by Subject
- Non-compliance with study drug
- Lost to follow up
- Study terminated by sponsor
- Transition to commercially available treatment
- Physician decision
- Disease relapse
- Symptomatic deterioration
- Protocol violation
- Start of a new anti-CLL therapy (with the exception of rituximab for the treatment of autoimmune hemolytic anemia) *
- Upon completion of a maximum of 24 cycles of CC-122 *
- For subjects on Arm B, subjects who have discontinued CC-122 prior to the maximum of 24 cycles and have received an additional 3 cycles of investigational supply of ibrutinib *
- Other

Similarly, the three reasons marked with “*” are allowed for study discontinuation in Protocol Amendment 7 and will be derived using corresponding standard wordings from the text field for “Other” specified reason: ‘Start of new anti-CLL therapy’, ‘Maximum number of CC-122 cycles completed’, ‘CC-122 discontinued, additional 3 cycles of ibrutinib completed’.

Protocol violations (PV) and protocol deviations (PD) will be identified and assessed by the clinical research physician or designee following company standard operational procedure. Protocol deviations and violations will be summarized by category and sub-category for the Safety population.

The following by-subject listing of subjects with demographic information included will be provided:

- Subject listing of discontinuation for any reason.
- Subject listing of screen failures.
- Subject listing of protocol violations and protocol deviations with an additional column to flag the protocol deviations that are identified as protocol violations.

7. DEMOGRAPHICS AND BASELINE CHARACTERISTICS

Demographics and baseline characteristics will be summarized by treatment arm, dose cohort, and overall for all populations defined in [Section 0](#), if not otherwise specified. Individual subject listings for the all enrolled subjects will be provided to support the summary tables.

7.1. Demographics

The continuous demographic variables, age (year), weight (kg), height (cm), Body Mass Index (BMI) (kg/m^2) and Body Surface Area (BSA) (m^2) will be summarized using descriptive statistics (e.g. n, mean, standard deviation, median, minimum, and maximum) by treatment arm, dose cohort and overall. BMI category ($<25 \text{ kg}/\text{m}^2$, $\geq 25 \text{ kg}/\text{m}^2$, Missing) will be summarized with frequency counts.

Age is calculated based on the date of birth and the date of informed consent. In the case date of birth is missing or partial, age collected in the Case Report Form (CRF) will be used. Age category (≤ 70 , > 70) will be summarized with frequency counts.

BSA (m^2) is calculated as follows:

$$\left(\frac{\text{Height (cm)} \times \text{Weight (kg)}}{3600} \right)^{1/2} \text{ (based on the Mosteller formula).}$$

BMI is calculated as follows:

$$\left(\frac{\text{Weight (kg)}}{(\text{Height (m)})^2} \right)$$

[figure not shown]
Race, sex and ethnicity will be summarized with frequency tabulations by treatment arm, dose cohort and overall.

7.2. Baseline Characteristics

Baseline clinical characteristics include temperature ($^{\circ}\text{C}$), systolic blood pressure (mmHg), diastolic blood pressure (mmHg), pulse rate (beats per minute [bpm]), respiration rate (breaths per minute [BPM]), overall interpretation of Electrocardiogram (ECG), ECOG performance status (0, 1 or >1), B-symptoms, disease diagnosis (CLL or SLL), current stage/prognostic classification and Minimal Residual Disease (MRD) (provided from eCRF).

The Cumulative Illness Rating Scale (CIRS) score will be documented by a qualified clinician at the time of the screening visit. The CIRS score will be collected to assess the performance status and fitness of subjects. Baseline CIRS will be presented as below:

- The total score category: 0, 1-3, 4-6, 7-9, 10-11, > 11 ;
- At least one grade 3 or higher comorbidities: Yes, No.

Baseline best corrected visual acuity, slit lamp examination results and ophthalmologic examination results will be summarized in an additional table for Safety population only.

For Safety population only, summary statistics will be provided for baseline Left Ventricular Ejection Fraction (LVEF), overall interpretation of LVEF, laboratory data (Hemoglobin [HGB]*, Potassium*, Total Bilirubin*, Aspartate Aminotransferase* [Aspartate Transaminase (AST) or serum glutamic oxaloacetic

transaminase (SGOT)], Alanine Aminotransferase* [Alanine Transaminase (ALT) or serum glutamate pyruvic transaminase (SGPT)], Lactate Dehydrogenase [LDH] , Uric Acid, Troponin-T, C-Reactive Protein, Direct Antiglobulin test, White Blood Cell (WBC) count*, ALC*, Absolute Neutrophil Count (ANC)*, Calcium*, Phosphorous, Serum Creatinine, Alkaline Phosphatase [ALP]*) and Creatinine Clearance. Frequency counts for NCI-CTCAE grades will be also provided for the laboratory tests above with asterisk sign (*).

Categorical baseline variables will be summarized using frequency counts and percentage by treatment arm, dose cohort and overall. Continuous baseline variables will be summarized by descriptive statistics in the same way as continuous demographic variables (e.g., n, mean, standard deviation, median, minimum, and maximum). Listings will be presented for all enrolled subjects.

7.3. Medical History

Medical history will be summarized by frequency counts and percentage for the Safety population. The summary will be tabulated by System Organ Class (SOC) and Preferred Term (PT) using the Medical Dictionary for Regulatory Affairs® (MedDRA) Version 22.0 or higher and presented by treatment arm, dose cohort and overall. Listings will be presented for all enrolled subjects.

7.4. Prior Therapies

The number of prior therapies for CLL/SLL collected in the CRF will be summarized for prior radiation therapies, prior systemic anti-cancer therapies and prior stem cell transplants separately by frequency tabulations for each treatment arm, dose cohort and overall for the Safety population. The therapies with the same sequence/regimen number are counted as one prior therapy. Listings will also be presented by treatment arm and dose cohort for all enrolled subjects.

Novel agent failure, information collected for resistance/intolerance of BTK inhibitor, PI3K inhibitor and Venetoclax, will be listed by treatment arm and dose cohort for all enrolled subjects.

8. STUDY TREATMENTS AND EXTENT OF EXPOSURE

Study treatment and extent of exposure summaries will be provided based on the Safety population. Descriptive statistics will be provided for treatment duration, number of cycles, cumulative dose, actual dose intensity and relative dose intensity by treatment arm, dose cohort and overall. Relative dose intensity is used in place of the treatment compliance. The distribution of treatment duration and number of cycles will be analyzed by frequency counts on different intervals of treatment duration and number of cycles.

For subjects in Arm A who switch treatment, the convention outlined in Section 5.1 will be applied. A by-subject listing will be provided for the subjects who received progressive disease subsequent treatment in Arm A.

8.1. Treatment Duration

Treatment duration is presented in days or weeks as appropriate. For each treatment arm the treatment duration is:

Arm A:

Treatment duration (days) = [(Last non-missing dose date of CC-122) - (First non-missing dose date of CC-122) + 1], where the first non-missing dose date of CC-122 is Cycle 1 Day 1.

Arm B:

CC-122 treatment duration (days) = [(Last non-missing dose date of CC-122) - (First non-missing dose date of CC-122) + 1], where the first non-missing dose date of CC-122 is Cycle 2 Day 1;

Ibrutinib treatment duration (days) = [(Last non-missing dose date of ibrutinib) - (First non-missing dose date of ibrutinib) + 1].

Arm C:

CC-122 treatment duration (days) = [(Last non-missing dose date of CC-122) - (First non-missing dose date of CC-122) + 1], where the first non-missing dose date of CC-122 is Cycle 1 Day 9;

Obinutuzumab treatment duration (days) = Minimal (28 days \times number of cycles of non-zero/non-missing Obinutuzumab dose, End of study date – First dose date of any IP +1.

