Ascending fixed-doses cohorts of CC-122 starting at 0.5 mg up to a maximum of 4.0 mg or NTD, whichever occurs first, in combination with obinutuzumab will be evaluated. After completion of the 0.5 and 1.0 mg fixed-dose cohorts, subsequent cohorts will be allowed to escalate in either 0.5 mg or 1.0 mg increments. Escalation to the next dose level requires 0/3 or $\leq 1/6$ DLTs at the current dose level. Further, an escalation increment of 1.0 mg requires the absence of any Grade 3 drug related non-hematologic AEs, any Grade 4 hematological event, and TLS or TFR of any grade at the current dose level. The SRC will make the recommendation of whether to open the next dose cohort and the incremental increase (0.5 or 1.0 mg) after review of the safety data of the current dose cohort (after full enrollment and completion of the DLT evaluation period).

CC-122 will be initiated on Cycle 1 Day 9 and administered on a 5/7-day schedule. For subjects on Arm C, Cycle 1 only will consist of 29 days to accommodate the 5/7-day schedule; subsequent cycles will consist of 28 days. Obinutuzumab will be administered intravenously on Cycle 1 Days 1, 2, 8, and 15 (see Section 8.2 for Treatment Description, Administration and Schedule). The dose of obinutuzumab on Day 1 and Day 2 of Cycle 1 may be adjusted per institutional practice provided the combined dose equals 1000 mg. Obinutuzumab will be administered on Day 1 every cycle thereafter up to Cycle 6.

CC-122 will be administered up to a maximum of 24 cycles of CC-122, or until disease progression, unacceptable toxicity, or discontinuation for any other reason, whichever is earlier. In the event CC-122 is discontinued prior to obinutuzumab, Celgene will continue to supply the protocol-specified total of 6 cycles of obinutuzumab. In addition, for patients that have surpassed the 24 cycles of CC-122, Celgene will continue to provide an additional 3 cycles of CC-122 to allow time for patients to be switched to commercially available therapies at the discretion of the treating physician.

Subjects will be observed for early DLTs for 28 days following initiation of CC-122 combination therapy (Cycle 1 Day 9 through Cycle 2 Day 8) (DLT evaluation period). Monitoring for late toxicities necessitating dose reductions or discontinuations will be conducted during Cycles 2 through 6.

Early DLT Evaluation of Intrasubject Dose Escalation Cohort in Arm A:

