8.2.9.2. Dose Modification Guidelines

Any IP-related toxicity meeting the definition of DLT will require dose reduction or interruption. The criteria for dose reduction are listed in [Table 14](#), should be used for dose modifications.

Chronic Grade 2 toxicity (other than specified below) may warrant dose reduction or interruption of one or both IP. Such cases should be discussed with the sponsor's medical monitor before changes are made.

Dose modification decisions for patients with cytopenia (below the lower limit of the normal range) at **baseline** will be based on the IWCLL guideline ([Table 13](#)). For patients with a normal neutrophil count, platelet count and/or hemoglobin value at baseline, the NCI CTCAE (version 4.03) will be used.

Any dose modifications must be recorded on the respective Study Drug Record eCRF.

Table 14: Dose Reduction Guidelines

Adverse Event	Grade	Action	Agent to be considered for interruption/reduction (in descending order)
Thrombocytopenia	≥ Grade 3	
• Hold all IP• Follow CBC at least every 7 days• If thrombocytopenia resolves to ≤ Grade 2, restart IP and reduce CC-122 to the next lower dose level. Ibrutinib may be restarted after thrombocytopenia resolves to ≤ Grade 1 or baseline at original dose after the 1st occurrence, and reduce by one dose level at each subsequent recurrence with a maximum of 2 dose reductions allowed. A 4th recurrence requires permanent discontinuation of ibrutinib.• Obinutuzumab should be restarted at the full dose after thrombocytopenia resolves to ≤ Grade 2, no dose reduction is allowed.	
• CC-122• Ibrutinib/obinutuzumab

Table 14: Dose Reduction Guidelines (Continued)

Adverse Event	Grade	Action	Agent to be considered for interruption/reduction (in descending order)

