8.2. Cumulative Dose and Dose Intensity

The cumulative actual dose and actual dose intensity for each study drug (CC-122, ibrutinib, obinutuzumab) will be presented by dose cohort for each arm. The actual dose intensity is defined as the cumulative actual dose divided by the total length of treatment for the IP.

CC-122:

The cumulative actual dose of CC-122 is defined as the sum of all doses of CC-122 taken across the treatment period.

The cumulative expected dose of CC-122 is calculated as below:

- For the cycles on daily schedule of CC-122 (only applicable to Arm A subjects):

Expected dose = (stop date - start date of CC-122 administration +1) \times planned daily dose;

- For the cycles on 5/7 days schedule of CC-122:

$$\text{Expected dose} = \text{Planned daily dose} \times \left[\left\lfloor \frac{\text{Dur}}{7} \right\rfloor \times 5 + \min \left(5, \text{Dur} - \left\lfloor \frac{\text{Dur}}{7} \right\rfloor \times 7 \right) \right], \text{ where}$$

Dur is the treatment duration for CC-122.

Repeat this derivation for each planned dose (i.e. take into account the dose escalation but not the decrease due to AE) and sum up.

The Expected dose intensity for CC-122 is the cumulative expected dose divided by the total length of treatment duration for CC-122.

Ibrutinib (Arm B)

The cumulative actual dose of ibrutinib is the sum of all doses of Ibrutinib taken across the treatment period. The cumulative expected dose of ibrutinib is the (planned daily dose \times Ibrutinib treatment duration in days). The expected dose intensity for Ibrutinib is the planned daily dose – 420 mg/day.

Obinutuzumab (Arm C):

The cumulative actual dose of obinutuzumab is the sum of all doses of obinutuzumab taken across the treatment period. The cumulative expected dose of obinutuzumab is the sum of the planned dose per Table 10 in the protocol Section 8.2.2.3 based on the last visit which has been completed:

Last visit completed	Cycle 1 Day 1	Cycle 1 Day 2	Cycle 1 Day 8	Cycle 1 Day 15	Cycle 2 Day 1	Cycle 3 Day 1	Cycle 4 Day 1	Cycle 5 Day 1	Cycle 6 Day 1
Cumulative expected dose (mg)	100	1000	2000	3000	4000	5000	6000	7000	8000

The Expected dose intensity for obinutuzumab is the cumulative expected dose divided by the total length of treatment duration for obinutuzumab.

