8.3. Relative Dose Intensity

Relative dose intensity is used in place of the treatment compliance. Relative dose intensity is defined as actual dose intensity divided by expected dose intensity.

Additionally, the number and percentage of subjects will be summarized by $\leq 80\%$ and $>80\%$ for relative total dose intensity of CC-122, for CC-122 and ibrutinib in Arm B, for CC-122 and obinutuzumab in Arm C, the actual category can be data driven.

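### Obinutuzumab relative dose intensity in Arm C cannot register delay: both intensities share one duration, so a subject given every infusion in full scores 100% however late

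*SAP*

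**What the plan says.** SAP 8.1 (Arm C) takes obinutuzumab duration as the minimum of two terms, in the expression containing "number of cycles of non-zero/non-missing Obinutuzumab dose, End of study date". The first term is 28 days multiplied by the number of cycles with a dose. The second is the calendar span from first dose of any study drug to end of study.

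SAP 8.2 then defines the two intensities:

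- Actual: "The actual dose intensity is defined as the cumulative actual dose divided by the total length of treatment for the IP".
- Expected: "The Expected dose intensity for obinutuzumab is the cumulative expected dose divided by the total length of treatment duration for obinutuzumab". The cumulative expected dose comes from a table of planned doses, "based on the last visit which has been completed", rising from 100 mg at Cycle 1 Day 1 to 8000 mg at Cycle 6 Day 1.

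SAP 8.3 combines them: "Relative dose intensity is defined as actual dose intensity divided by expected dose intensity". It also gives the result a role beyond exposure: "Relative dose intensity is used in place of the treatment compliance". Subjects are classed as ≤80% or >80%.

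On the protocol side, obinutuzumab dose reduction is not allowed (Protocol 8.2.9 and 8.2.12.3), and holds end in a full dose. For example, Table 14 says "Obinutuzumab should be restarted at the full dose after thrombocytopenia resolves". For Arm C, Protocol 4.1 says that "Cycle 1 only will consist of 29 days to accommodate the 5/7-day schedule"; later cycles are 28 days.

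**The concern.** Dose intensity is dose per unit of time, and RDI is meant to show how far delivery fell behind the planned rate. That requires actual time in one intensity and planned time in the other. Here both use the same length, and the expected dose advances with visits rather than with the calendar, so no part of the ratio responds to lateness.

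Delay is a foreseeable way for obinutuzumab delivery to suffer in this arm, because doses cannot be reduced and are resumed in full after a hold. SAP 8.4 itself provides for cycles being postponed. SAP 17.2.2 ends each cycle on the day before the next one starts, so an actual cycle can exceed the fixed 28 days of SAP 8.1.

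Tolerability of the combination is a primary objective. The statistic offered in place of compliance for the partner drug would not show one of the main signs of poor tolerability.

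**Working it through.** **Reproducing the SAP's figure.** Planned doses from Protocol 8.2.2.3 are 100, 900, 1000 and 1000 mg in Cycle 1, then 1000 mg in each of Cycles 2 to 6. The running sum is 100, 1000, 2000, 3000, 4000, 5000, 6000, 7000, 8000 mg. This matches every entry of the SAP 8.2 table and counts nine infusions.

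**The algebra.** Let A be the cumulative actual dose, E the cumulative expected dose and D the SAP 8.1 duration.

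RDI = (A/D) / (E/D) = A/E, for any D.

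The minimum in SAP 8.1 makes no difference, and a calendar duration used in both places would cancel too. The cause is the shared denominator together with a visit-indexed E. The cycle count in SAP 8.1 is not the cause.

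**Under the SAP.**

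- All nine infusions in full over six cycles, with total delay of 0, 14, 28, 42, 56, 84 or 140 days: D = 6 × 28 = 168 and RDI = 8000/8000 = 100% each time.
- One 1000 mg infusion omitted, Cycle 6 Day 1 completed: RDI = 7000/8000 = 87.5%. Omissions do show.

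**On elapsed time.** Planned time for six cycles is 29 + 5 × 28 = 169 days. With full doses and total delay d, RDI = (8000/(169 + d)) / (8000/169) = 169/(169 + d). The delays are assumptions; the documents give no figure.

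| Assumed delay (days) | SAP RDI | Elapsed-time RDI |
|---|---|---|
| 28 | 100% | 169/197 = 85.8% |
| 42 | 100% | 169/211 = 80.1% |
| 56 | 100% | 169/225 = 75.1% |
| 84 | 100% | 169/253 = 66.8% |

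The ≤80% class is reached when d ≥ 169/0.8 − 169 = 42.25 days, that is, at 43 whole days (42 if planned time is taken as 168).

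**Absolute intensity.** This is a separate effect, and it does come from SAP 8.1. With 56 days of delay the SAP gives 8000/168 = 47.6 mg/day; elapsed time gives 8000/225 = 35.6 mg/day, against a planned 8000/169 = 47.3. Ignoring the 29-day Cycle 1 costs one day in 169, about 0.6%, and cancels in the RDI.

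**Contrast with CC-122.** Its duration in SAP 8.1 is the calendar span from first to last dose, and its expected dose in SAP 8.2 grows with that span. Take 120 planned doses on the 5/7-day schedule at a constant planned dose (last dose on Day 166) with 84 days of holds. The span is 166 + 84 = 250 days and the expected count is 35 × 5 + 5 = 180, so RDI = 120/180 = 66.7%. The ibrutinib expected dose is also planned daily dose times calendar duration. Arm C tables would therefore carry two quantities under one name, only one of which responds to delay.

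**The case against.** The strongest reply is that interruptions are reported elsewhere. SAP 8.4 defines dose delay and summarises subjects with interruptions, interruptions due to AEs and time to first interruption. SAP 11.1.1 tabulates TEAEs leading to obinutuzumab interruption, and SAP 6 summarises reasons for discontinuing each drug. This stands in part: a reader of the report would learn that interruptions occurred. Their length is not clearly recovered, because the total-days item in SAP 8.4 is worded for CC-122 and ibrutinib.

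Second, this is a descriptive summary. The DLT, NTD and MTD rules, the late-toxicity rule and the efficacy analyses do not use RDI. That stands in full and limits the weight of the point.

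Third, moderate delay would not change a subject's class: at 28 days the elapsed-time RDI is still about 86%, and SAP 8.3 lets the categories be data driven. That stands too, so the class shift should be read as an illustration.

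A reader might infer more than the documents support:

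- That Arm C must show near-perfect delivery whatever happens. It need not, since omitted or incomplete infusions lower the RDI.
- That delay is the only change to obinutuzumab short of stopping. Table 14 also allows slower or interrupted infusions.
- That the CC-122 RDI is faulty because it ignores AE-driven reductions. SAP 8.2 excludes them expressly, which lets RDI show dose lost to toxicity. That is a defensible choice.

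**Conclusion.** The point holds for obinutuzumab in Arm C. As written, its RDI is a ratio of milligrams and contains no time, so delay with full doses always scores 100%. The SAP 8.1 duration also overstates absolute mg/day after delays.

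The cancellation follows from the SAP text alone, reading the treatment length in the actual intensity as the drug-specific duration of SAP 8.1. That is the natural reading, because SAP 8.2 presents intensity drug by drug. The sizes (about 86% down to 67% for 28 to 84 days, with the ≤80% class reached at about 42 to 43 days) rest on assumed delays with all nine infusions given in full.

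The consequence is confined to the descriptive exposure and compliance summary. It is worth correcting because that summary stands in for compliance and bears on the tolerability of the combination, but it does not put the dose-finding or efficacy conclusions in doubt.

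**What to change.** For obinutuzumab intensity, replace the shared duration with two lengths:

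- Actual length = (start date of the last dosed cycle − first infusion date) + planned length of that cycle (29 days for Cycle 1, otherwise 28). Take the start as the first obinutuzumab infusion in that cycle, because SAP 17.2.2 lets any study drug open a cycle.
- Planned time = 29 days for Cycle 1 plus 28 for each later cycle through the last dosed cycle.
- Expected intensity = cumulative planned dose (the existing SAP 8.2 table) / planned time.
- RDI = (cumulative actual dose / actual length) / expected intensity.

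Checks: with no delay, Cycle 6 starts 29 + 4 × 28 = 141 days after the first infusion, so actual length is 141 + 28 = 169 and RDI is 100%. With 56 days of delay it is 169/225 = 75%. A subject who receives Cycle 1 on time and stops after Day 15 has (3000/29)/(3000/29) = 100%.

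The simpler length, last minus first infusion date plus 28, should not be used. The same Cycle 1 subject would get 14 + 28 = 42 days against 29 planned, an RDI of 29/42 = 69% with no delay at all. One limit remains: a late infusion within Cycle 1 in a subject who never reaches Cycle 2 is still not seen.

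Extend the total-days-of-interruption summary in SAP 8.4 to obinutuzumab. The cost is SAP wording and a small program change using infusion dates already collected.
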